Physical activity has frequently been suggested as beneficial for sarcoidosis patients (NHS, 2015a). This is due to a host of specific and non-specific benefits to those with the condition. This includes the overall improvement to health including decreased levels of non-communicable diseases as well as lower the risk of depression (NHS, 2015b). Although anyone can suffer from depression, sarcoidosis patients have been shown to have increased levels (Hinz et al., 2012). In addition, physical activity helps not only to slow and stop deconditioning; a major issue within sarcoidosis (Fleischer et al., 2014), but also aids the reversal of this process (Strookappe et al., 2015). However, the condition lacks specific guidelines, unlike similar conditions such as COPD and asthma (ACSM, 2014; National Institute of Health and Care Excellence (NICE), 2016). Due to this, sarcoidosis patients are often given advice on exercise and other forms of physical activity such as walking or dancing that are not underpinned by research specific to their condition and as such are potentially dangerous exercise programmes/advice. Holland et al. (2015) states the unique presentation of ILD, including sarcoidosis, requires modifications of exercise prescription for individuals, which was noted as a key issue by Strookappe et al. (2016) in a systematic review of physical activity and training in Sarcoidosis. In addition to this, the effect of pulmonary sarcoidosis on exercise capacity and strength in comparison to a healthy population is limited and needs further research. Reductions to both exercise capacity and muscle strength indicated by lower results than normative values, are known primary symptoms of Sarcoidosis (Spruit, 2005; Hildebrand et al., 2012; Baughman, 2013),

which continue to get progressively worse with the onset of secondary symptoms such as deconditioning (Mitchell et al., 2012; Fleischer et al., 2014). The symptoms of sarcoidosis, in tandem with the varied manifestations (Skin, liver, heart etc. (Saidha et al., 2012)) of the disease alongside pulmonary, make it incredibly hard for accurate, suitable suggestions for physical activity, especially when considering the current lack of literature. This is highlighted by the role of fatigue within sarcoidosis, which is recognised as a major factor within the disease (Baughman, 2013) and therefore needs considering when creating an exercise prescription plan.

Therefore, increased understanding of the effects of pulmonary sarcoidosis is needed as well as comparison to a healthy age matched control population to allow for the data to be compared alongside other intestinal lung diseases (ILD). Further research into this area is vital as exercise training has been shown to be in some cases just as/more effective than medical treatment across a wide range of chronic conditions (Pedersen & Saltin, 2015). Marcellis et al. (2013) argues rehabilitation should be utilised alongside any pharmacological treatment despite the need for future research on potential benefits. Strookappe et al. (2016) also states further random controlled trials are needed but the effects of physical training seem promising from the current limited research.

Despite Sarcoidosis affecting a significant number of people globally, being second only to asthma in young adults for respiratory diseases (Morgenthau & lannuzzi, 2011), there is a short supply of research into the condition as well as novel treatments to alleviate the primary and secondary symptoms. Therefore therapies (diet and physical activity) are required to help the condition but also prevent further reductions in QOL.

Aim: The primary aim of this study is to ascertain the physical activity patterns and baseline parameters in those with pulmonary sarcoidosis with regards to perceived physical activity and actual physical activity. The secondary aim of the study is to investigate the effect of pulmonary sarcoidosis in relation to muscle strength and exercise capacity against physical activity, lung function and oxygen saturation and how these differ from healthy normative values.

Primary Outcome: Daily physical activity measures against self-reported (IPAQ). **Secondary Outcome**: Demographic data and clinical status (age, gender & ethnicity); Body fat percent, Lung function (forced vital capacity), functional exercise capacity assessed by six-minute walk test, muscle strength by isokinetic dynamometer and hand dynamometer. Patient reported health status and pulmonary complaints objectified in disease-specific quality of life: Sarcoidosis Health Questionnaire and fatigue score (Fatigue Assessment Scale (FAS).

Participants

Participants with medically diagnosed pulmonary sarcoidosis will be selected. They will be recruited through support groups and online forums from the known sarcoidosis population. A diagnosis of sarcoidosis will be accepted provided the participant has diagnosed pulmonary sarcoidosis ascertained by self-reporting. Patients will be prospectively recruited following new diagnosis of non-cardiac sarcoidosis. (1 in 10,000 have sarcoidosis of which 90% is pulmonary). Due to lack of research into sarcoidosis, there is not enough evidence to permit accurate power calculations, however, based on previous studies and the proportion of diagnosed cases, n=15 participants will be aimed for and act as a pilot for a larger randomised control trial (power 0.80 [80%], significance P<0.05) excluding drop-out.

Inclusion Criteria:

- Patients with known Sarcoidosis according to ATS/ERS/ WASOG criteria statement
- Age: 18-65 years Both males and females
- Written informed consent is obtained.
- Access to a computer with Internet

Exclusion Criteria:

- Contraindications to (not able to perform) physical tests or exercise testing - e.g. unstable cardiovascular disease, oncological, cardiac, neurological or orthopedic history making them unable to participate screened by a sub-maximal fitness screening form.

- An injury in the past 6 months that inhibits ability to perform exercise testing by a submaximal fitness screening form.

- Patients with a concurrent and predominant diagnosis of another significant respiratory disorder (for example: asthma, chronic obstructive pulmonary disease (COPD), cystic fibrosis, or lung cancer) by a sub-maximal fitness screening form.

- Pregnancy

- Physical disability (non-ambulatory patient e.g. wheelchair or bed-bound)

- Inability to obtain informed consent

- Cognitive failure making them unable to give consent or understand questionnaires or instruction.

Experiment Design

This is a prospective cross-sectional observational project, with no intervention. Observational exercise testing will include endurance exercise and muscle strength. Patients participating in this study will be treated according to current guidelines (ATS/ERS/ WASOG). As such, diagnostic procedures or treatment will not be postponed or impacted on by participation in this study. All data will be self-reported and self-referred for voluntary participation. Participants will be invited to attend the laboratory for testing on two occasions to measure physical activity, fatigue, aerobic fitness and muscular strength with exercise testing at the Human Performance lab, Kingston University, London to establish the influence on symptoms, physiological and psychological outcomes. Exercise testing will follow standard guidelines (ACSM, 2016). Travel cost reimbursement will be offered to all participants who attend lab visits.

Appropriate health and risk stratification screening will be performed via a submaximal exercise screening form (appendix XI) and any participant with an injury in the past 6 months or a known contraindication (ACSM, 2014) to exercise will be excluded from the study. Inclusion criteria are based on having pulmonary sarcoidosis, aged 18 years or above, and participants may have other forms too but must have pulmonary sarcoidosis.

1. During the two laboratory visits to the Human Performance Lab, patients reported response will be objectified by three standardized questionnaires (IPAQ, SHQ and FAS), pulmonary function tests, mass and stature laboratory data will be recorded.

2. The patient is asked to keep a daily record physical activity by wearing a triaxial accelerometer on their hip to measure daily physical activities and ambulatory movements for 7 days.

Lab Procedures

During visit one, participants will sign informed consent forms (appendix II) and have any questions answered before continuing. They will then be put through a screening process beginning with physical examination: characteristics such as anthropometric data (stature, mass, heart rate (HR), blood pressure, age, BMI, fat% (Bodpod, Cosmed/ Bioelectric Impedance Analysis (BIA), Tanita) will be collected. Following this, participants will conduct a lung function test via computer spirometery (Oxycon Pro, VIASYS GmbH, Eric Jaeger, Hoechberg, Germany), their predicted results will be corrected for ethnicity (Bellamy, 2005) allowing an accurate percentage of lung function to be recorded. Caucasian results remain the same, whilst Black-Caribbean are decreased by 13% (Bellamy, 2005). Participants will then conduct muscle strength testing of key muscle groups using an isokinetic dynamometer (Biodex System 4, Biodex Corporation, NY, USA); tests include: elbow flexor muscle strength (EFMS), quadriceps peak torque (QPT) and hamstring peak torque (HPT). In addition to this handgrip strength will also be assessed via handgrip digital dynamometer (Accord Medical Products). A minimum rest period of 20 minutes will follow (Vainshelboim et al., 2014) based on exercise-based pulmonary rehabilitation research. Heart rate (bpm) will be checked at the end of this period and in two minute intervals until HR returns to baseline as per ACSM (2014) guidelines. Physical testing will not take place until this return to baseline. Following this rest period participants will conduct a sixminute walk test (6MWT) during the test participants will be measured for Borg rate of perceived exertion and Borg Dyspnoea at 2 minute intervals and at completion of the test and oxygen saturation levels of participants will be recorded during the 6MWT via a portable pulse oximeter. Once the 6MWT has been completed participants will complete three guestionnaires, the fatigue assessment scale (FAS; De Vries et al., 2004), international physical activity questionnaire (IPAQ; Ekelund et al., 2003) and Sarcoidosis Health Questionnaire (SHQ; Cox et al., 2003). Before leaving, participants will be given tri-axial accelerometers (GT3X+ accelerometer, Actigraph), which will be used to measure the participants physical activity (PA) for seven days, to establish habitual physical activity levels and compare against the results of the IPAQ.

During the second lab visit, participants will return their accelerometers and follow the same pattern of testing from the first visit, excluding the questionnaires (SHQ, FAS & IPAQ) and anthropometric information. The order of testing will follow ACSM (2016)

guidelines therefore strength and aerobic/anaerobic capacity will be first. Alongside this, age-matched healthy participants with no known interstitial lung disease (ILD) or other condition linked to reduced physical activity will used as a comparison between sarcoidosis and healthy populations.

Statistical analysis

A mixed model repeated measures analysis of variance (ANOVA) will be utilized, in addition to correlations and regressions.

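### The inclusion list requires ATS/ERS/WASOG-defined sarcoidosis, but the diagnosis is taken on self-report with no described check, and the population is defined inconsistently

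*Combined protocol and SAP*

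**What the plan says.** The combined protocol and SAP describes who is to be studied in several places.

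- The Aim is to "ascertain the physical activity patterns and baseline parameters in those with pulmonary sarcoidosis".
- Participants opens with "Participants with medically diagnosed pulmonary sarcoidosis will be selected".
- On the source of volunteers it says: "They will be recruited through support groups and online forums from the known sarcoidosis population".
- On ascertainment it says: "A diagnosis of sarcoidosis will be accepted provided the participant has diagnosed pulmonary sarcoidosis ascertained by self-reporting".
- The next sentence reads: "Patients will be prospectively recruited following new diagnosis of non-cardiac sarcoidosis".
- The disease bullet in Inclusion Criteria reads: "Patients with known Sarcoidosis according to ATS/ERS/ WASOG criteria statement". None of the four bullets names the lung.
- Experiment Design restates eligibility and adds that "participants may have other forms too but must have pulmonary sarcoidosis". It also says: "All data will be self-reported and self-referred for voluntary participation".

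Lab Procedures describes a visit 1 screening process of consent, physical examination and body measurements, followed by spirometry, strength testing, the walk test and questionnaires. Visit 2 repeats the physical tests. Neither visit includes a look at a clinic letter, medical record, imaging or histology.

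**The concern.** A published criteria statement is a clinical standard. A volunteer from a forum can report having been told of a diagnosis, but that report does not show that the standard was met. If the plan is followed exactly, the eventual report will have no basis for saying that participants satisfied ATS/ERS/WASOG criteria.

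The definition is also split between the bullets and the prose, and the two have not been kept in step. Lung involvement is in the prose only. A separate sentence points to newly diagnosed, non-cardiac cases, although the bullet speaks of known disease.

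The results most exposed belong to the secondary aim: the contrasts with healthy participants, and the relations of strength and exercise capacity to lung function and oxygen saturation. The study is also meant as a pilot for a randomised trial, so an unclear case definition could carry forward.

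**Working it through.** **1. The plan's own figure.** The target is n = 15, printed beside 80% power and P<0.05. It cannot be reproduced: no effect size, standard deviation, test or drop-out rate is given, and the protocol itself says that accurate power calculations are not possible. Back-solving with the noncentral t distribution (two-sided 5%, 80% power), 15 participants would detect a standardised paired difference of 0.78. With an assumed 15 controls (the number is not stated), they would detect a two-group difference of 1.06 SD. The eligibility point does not depend on these values.

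**2. Standard against method of ascertainment.**
- Standard (Inclusion Criteria): sarcoidosis by a named criteria statement.
- Method (Participants): the participant's own report of a diagnosis.
- Link between them: none described. The sub-maximal screening form is assigned to contraindications, injury and other respiratory disease. Spirometry is an outcome with no eligibility threshold.

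The criteria claim therefore rests entirely on what the participant says.

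**3. The population statements side by side.**
- Lung involvement required: Participants (opening sentence and self-report sentence) and Experiment Design.
- Lung not mentioned: the inclusion bullets and the new-diagnosis sentence.
- Timing: known disease in the bullet, new diagnosis in the sentence.
- Extent: other forms allowed in Experiment Design, non-cardiac only in the new-diagnosis sentence.

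Age shows that the two statements of eligibility are out of step: the list gives 18–65 years, while Experiment Design sets 18 as a lower limit with no upper one.

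**4. Possible effect on a patient–control contrast.** Suppose k of n patients are misclassified and have the control mean. Then

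expected observed difference = (1 − k/n) × true difference.

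With n = 15:
- k = 1: 1/15 = 6.7% shrinkage
- k = 2: 2/15 = 13.3%
- k = 3: 3/15 = 20%

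With k = 2, keeping an expected difference of 1.06 SD would need a true difference of 1.06 ÷ (13/15) = 1.22 SD, ignoring any change in spread. The values of k are illustrative, because the documents give no error rate.

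**5. A counterfactual.** If the bullets were applied alone, and volunteers were a random draw from a population with the protocol's 90% pulmonary share:
- P(at least one non-pulmonary) = 1 − 0.9^15 = 79%
- P(at least two) = 1 − 0.9^15 − 15 × 0.1 × 0.9^14 = 45%

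For an assumed share of 80% to 95%, the first probability runs from 96% down to 54%. This is not how the protocol as a whole reads. With the prose requirement applied, the intended share is 100%, and what remains is error in self-report.

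**The case against.** The strongest reply is that the bullet and the self-report sentence do different jobs. One says what counts as disease and the other how it is learned, and a participant may truthfully report a diagnosis that a clinician made under those criteria. The text also asks for medically diagnosed disease, so unverified by the study does not mean undiagnosed. Self-report is a common feasibility choice in a small pilot without intervention, and the screening form in the appendix, which is not in the text reviewed, might ask about diagnosis. Much of this stands: the two statements can coexist. They do not supply verification, however, and an answer on a form would still be self-report.

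A reader might infer from the bullets that someone with skin or liver sarcoidosis alone could be enrolled, so that the sample may not be a pulmonary one. The documents do not support that. Participants and Experiment Design both require pulmonary disease, so the omission is a drafting gap.

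A reader might also take 6.7% to 20% as the expected dilution. That does not hold either. The Background describes reduced exercise capacity and strength as features of sarcoidosis generally, so a person with non-pulmonary disease would probably not resemble a healthy control. The primary outcome compares each person's accelerometer record with the same person's IPAQ, and this dilution does not apply to it.

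**Conclusion.** The point holds in a limited form. The plan cites a criteria-based diagnosis, accepts self-report and describes nothing that connects the two, so it cannot support a claim that participants meet ATS/ERS/WASOG criteria. The missing lung requirement in the bullets and the sentence on new, non-cardiac diagnosis are inconsistencies to be reconciled. They do not show that the protocol admits non-pulmonary patients.

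The size of any bias is unknown. A loss of 6.7% of a patient–control difference per misclassified entrant is an upper-end illustration, resting on 15 patients and on such entrants having the control mean. The effect falls mainly on the secondary contrasts and lung-function correlations. For the primary comparison, what is at stake is how the population is described. The conclusion on verification assumes that no appendix contains a check that the main text leaves out.

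**What to change.** State one population definition in the inclusion list, in line with Experiment Design: pulmonary sarcoidosis, with other forms allowed. Reconcile or delete the sentence on new, non-cardiac diagnosis; if either restriction is intended, it belongs in the list. Then choose one of two routes.

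- **(a) Verify.** Confirm the diagnosis from an existing clinic letter or discharge summary seen at visit 1, and delete the acceptance of self-report alone. Keep the ATS/ERS/WASOG wording only if the letter supports it, since a letter naming pulmonary sarcoidosis need not show that the criteria were met.
- **(b) Relabel.** Keep self-report, remove the ATS/ERS/WASOG claim, and describe the population throughout as self-reported pulmonary sarcoidosis.

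Both routes need a wording amendment; neither adds a test. Route (a) may delay or lose a few volunteers who have no paperwork, requires handling of identifiable medical letters, and means amending the statement that all data are self-reported. Route (b) costs little to run but narrows what the results can be said to describe.

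### Does the 80% power label beside n=15 overstate what this pilot can detect?

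*Combined protocol and SAP*

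**What the plan says.** The Participants section explains the sample size in one sentence. It first concedes that "there is not enough evidence to permit accurate power calculations". It then cites unnamed earlier studies and the share of cases that are diagnosed, and says that "n=15 participants will be aimed for and act as a pilot for a larger randomised control trial (power 0.80 [80%], significance P<0.05) excluding drop-out". The earlier studies' figures are not given, and neither is a drop-out rate.

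The other relevant statements stand elsewhere and are not tied to this number:

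- The Primary Outcome is "Daily physical activity measures against self-reported (IPAQ", a comparison within each person of accelerometer activity with questionnaire activity.
- Lab Procedures adds a healthy group: "age-matched healthy participants with no known interstitial lung disease (ILD) or other condition linked to reduced physical activity will used as a comparison". Its size is not stated.
- Statistical analysis reads, in full: "A mixed model repeated measures analysis of variance (ANOVA) will be utilized, in addition to correlations and regressions".
- Experiment Design describes a cross-sectional observational project without an intervention.

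**The concern.** A power figure means something only for a named outcome, effect, variability and test. Here none of these is given, and the figure shares a sentence with an admission that power cannot be calculated accurately. Read as a property of the 15 participants, the two halves of the sentence pull against each other.

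The risk would be one of interpretation. If readers believe the study has 80% power in general, they could take a non-significant result in 15 people as good evidence of no difference or no association. For many plausible effects it would not be, and for the comparison with healthy volunteers no power can be stated at all while their number is unknown.

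**Working it through.** **Can the plan's own figure be reproduced?** No. The stated inputs are n=15, power 0.80 and a significance level of 0.05 (all from Participants). The effect size, standard deviation, correlation, test and sidedness are absent. With no calculation shown, none can be found in error. What can be checked is whether 80% is attainable at n=15, and for what effect.

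**Assumptions, not in the protocol:** two-sided tests, normal data, 15 completers.

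**Paired comparison** (the form closest to the primary outcome). Power comes from the noncentral t distribution with n−1 = 14 degrees of freedom and noncentrality d√n, where d is the mean difference divided by the SD of the differences.

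- d = 0.8: noncentrality 0.8 × √15 = 3.10; power 0.821.
- d = 0.5: noncentrality 0.5 × √15 = 1.94; power 0.438. Reaching 80% here would take 34 pairs.
- 80% power is reached at d = 0.778.
- Normal-approximation check: (1.960 + 0.842)/√15 = 2.802/3.873 = 0.72, slightly optimistic as expected at this size.
- One-sided, the 80% threshold falls to d = 0.68.

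**Correlation.** By Fisher's z, 80% power needs r = tanh(2.802/√12) = tanh(0.809) = 0.67. Simulation of the usual t-test of a correlation gives power of about 0.19 at r = 0.3, 0.50 at r = 0.5 and 0.80 at r = 0.65.

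**Precision.** The 95% confidence interval half-width for a mean within-person difference is t(0.975, 14)/√15 = 2.145/3.873 = 0.55 SD of the differences. If 12 of 15 completed (an assumed figure), it would be 2.201/√12 = 0.64 SD, and the paired 80% threshold would rise to d = 0.89.

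**Comparison with healthy volunteers.** If there were 15 of them (assumed), 80% power would need d = 1.06. This illustrates the design only. The missing number of controls is a separate omission and does not bear on whether the 80% label is right.

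**The two readings of the sentence.**

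1. The bracket belongs to the later trial. It stands directly after the mention of that trial, so this is the natural grammatical reading. Nothing is then claimed about the power of 15 people, and the opening disclaimer and the bracket do not conflict.
2. The bracket belongs to n=15. The closing words on drop-out fit this reading better. The claim is then unsupported but attainable: a paired test at d = 0.8 needs exactly 15 pairs, since 14 give 0.790 and 15 give 0.821.

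Neither reading yields a figure that the protocol's own content contradicts.

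**The case for a change.** The strongest case for acting is that neither reading is satisfactory. If the label describes n=15, it lacks support and clashes with the start of its own sentence. If it describes the later trial, this study has no power or precision statement, and the later trial's size is not given either. A pilot needs no power claim, so removing an unsupported one costs only words. Even the favourable paired case is fragile: one drop-out takes it just below 80%. A correlation of 0.5, large by the usual convention, has only 50% power, and the protocol never says that the paired case is the one it means.

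Much of this stands as a description. The label is ambiguous, its inputs are missing, and 15 people can reliably detect only big effects. It does not establish an error. Power is ordinarily stated for the primary outcome, and the protocol nowhere claims 80% for the correlations, regressions, mixed model and control comparison together. Every quoted shortfall comes from an effect size or a number of controls supplied from outside the document.

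There is also a limit on the paired calculation. A standardised difference between accelerometer and questionnaire activity needs the two on a common scale, which the protocol does not define. If agreement is the target, power to detect a mean difference is not the right quantity. That cuts both ways: it weakens the figures that make 80% look attainable as much as those that make it look inflated.

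**Conclusion.** The concern is right that the label is unsupported and ambiguous, but no change to the plan follows. The 80% is not shown to be wrong: under two-sided testing at 0.05 with 15 completers and normal data, a paired comparison reaches it at d of about 0.78 and a correlation at r of about 0.65. The statement that it falls short, for example 44% at a paired d of 0.5, depends on effects that the protocol neither states nor claims to detect.

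This is a gap in explanation, and readers can fill it sensibly. The study is an observational pilot whose protocol says openly that accurate power calculations were not possible. Saying which study the bracket describes would leave the target of 15, the measurements and the analyses as they are. An analyst would report estimates with confidence intervals, expecting a half-width of about 0.55 SD of the within-person differences with 15 completers, and would not treat a non-significant result as evidence of no effect. The conclusion would need another look only if the sponsor used the 80% to support a negative finding in these 15 people.

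### FAS and SHQ are completed after the six-minute walk with no stated recovery, so acute exertion may carry over into two named secondary outcomes

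*Combined protocol and SAP*

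**What the plan says.** Lab Procedures sets the visit-one order: consent, anthropometry, spirometry, strength testing, rest, six-minute walk test (6MWT), questionnaires, issue of the accelerometer.

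- Strength: "Participants will then conduct muscle strength testing of key muscle groups using an isokinetic dynamometer", plus handgrip.
- Protection of the walk: "A minimum rest period of 20 minutes will follow", heart rate is checked until it is back to baseline, and "Physical testing will not take place until this return to baseline".
- During the walk: "Borg rate of perceived exertion and Borg Dyspnoea at 2 minute intervals and at completion of the test".
- After the walk: "Once the 6MWT has been completed participants will complete three guestionnaires", namely the FAS, the IPAQ and the SHQ. No interval or recovery condition is attached.

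The visit-two paragraph of Lab Procedures repeats the testing pattern but leaves out all three questionnaires and the anthropometry. It adds that the order of testing follows a cited guideline, with strength and aerobic or anaerobic capacity first. Item 1 of Experiment Design, by contrast, lists the three questionnaires among the measurements at both laboratory visits.

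The SHQ and the "fatigue score (Fatigue Assessment Scale (FAS" are named secondary outcomes. The background refers to "the role of fatigue within sarcoidosis, which is recognised as a major factor within the disease". Statistical analysis names a mixed-model repeated-measures ANOVA and adds correlations and regressions without naming variables.

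**The concern.** The plan recognises that exertion can carry over from one assessment to the next, and it guards the walk against this. It gives no such guard to the fatigue scale, which is arguably the assessment most open to it. The heart-rate rule governs physical testing, and questionnaires are not physical testing.

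Three uses of the scores are exposed:

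- **Absolute levels.** If people report more fatigue or worse health after a walk than at rest, the levels described for this population are shifted, and so is any comparison with published norms.
- **Patient-control contrasts.** If controls complete these questionnaires and find the tests less taxing, the shift differs between groups and appears as a disease effect.
- **Correlations.** If those who find the walk hardest shift most, the procedure itself creates an association between fatigue and walk performance. With no rested score, the data could not separate it from a feature of the disease.

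The Participants section calls the study a pilot for a larger randomised trial, so the order could be carried forward.

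**Working it through.** **Sequence check.** The documents contain no figure on this point to reproduce, so the first step is to compare what precedes each assessment.

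| Assessment | Preceded by | Recovery stated |
|---|---|---|
| 6MWT | Strength tests | At least 20 minutes, and heart rate back to baseline |
| FAS, IPAQ, SHQ | 6MWT | None |

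**Is there a rested measurement?** On the visit-two paragraph, no, because the questionnaires are not repeated. On Experiment Design, there is a second administration, but no order within the visit is given. Visit two follows the visit-one pattern, so a repeat would probably also come after exercise. Neither section supplies a score known to be taken at rest.

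**Illustration 1: correlation within patients.** Inputs: n = 15 (Participants section). Assumed, with no support in the documents: a true correlation of zero; a shift of b SD of FAS per SD of worse walk performance, with b from 0.2 to 0.5; and a higher FAS score meaning more fatigue.

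The observed FAS is the true score (SD 1) minus b times walk performance (SD 1), so the induced r = -b/√(1 + b²).

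- b = 0.2: -0.2/√1.04 = -0.196
- b = 0.5: -0.5/√1.25 = -0.447

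The two-sided 5% critical |r| at n = 15 is about 0.51, so both values fall below it. By Fisher z, with standard error 1/√12, the chance of declaring significance is:

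- r = -0.196: z = 0.199 × √12 = 0.69, giving about 11%
- r = -0.447: z = 0.481 × √12 = 1.67, giving about 38%

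The nominal rate is 5%.

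**Illustration 2: patients against controls.** Assumed: 15 controls (the number is not stated), controls completing the same questionnaire, unit SD, no true difference, and patients shifted by δ SD more than controls. The standard error is √(2/15) = 0.365. The rejection rate is Φ(δ/0.365 − 1.96) + Φ(−δ/0.365 − 1.96).

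| δ | Rejection rate |
|---|---|
| 0.1 | 5.9% |
| 0.2 | 8.5% |
| 0.3 | 13% |
| 0.5 | 28% |

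An equal shift in both groups gives δ = 0 and returns the nominal 5%, but absolute levels remain biased.

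**The case against.** Much of the case on the other side stands, and it limits what can be claimed.

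- A reader might infer that these scores do measure acute exertion. The documents do not show that. They give neither the recall period nor the item wording of FAS or SHQ, and an instrument that asks about usual state or past weeks would be less exposed.
- A reader might infer that the questionnaires come straight after strength testing. They do not: the rest, the heart-rate criterion and the walk lie between. Even after the walk, immediacy is inferred from the absence of a stated interval.
- A single administration is not settled, because Experiment Design and the visit-two paragraph conflict.
- No correlation of fatigue with the walk is specified. The secondary aim relates strength and exercise capacity to physical activity, lung function and oxygen saturation. A fatigue analysis is permitted by the open wording of Statistical analysis but not named there.
- The -0.20 to -0.45 range only converts an assumed slope into a correlation. It is not evidence that the effect exists.
- A reader might extend the point to the primary outcome, since the IPAQ is completed at the same moment. Nothing in the documents shows that the IPAQ is affected.

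Two other defences do not hold. The Borg ratings allow a check on whether scores track exertion in the walk, but they cannot recover a rested score. The rule placing strength and aerobic capacity first does not block a change, because anthropometry and spirometry already precede strength testing at visit one.

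**Conclusion.** The point holds as an uncontrolled risk, not as a demonstrated bias. As written, visit one takes FAS and SHQ after the 6MWT with no stated recovery, and no section provides a score known to be taken at rest. Contamination of two secondary outcomes is possible. Its size cannot be determined from the documents, and the figures above are conditional on assumed shifts, an assumed scoring direction and an assumed control group. The change is worth making because it removes the risk at almost no cost. Confidence is medium, chiefly because the recall wording is not given.

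**What to change.** 1. At visit one, give FAS, SHQ and any IPAQ completed at that visit after consent and before spirometry, strength testing and the 6MWT.
2. Use the same order for controls, for any questionnaire they complete.
3. Reconcile Experiment Design with the visit-two paragraph on whether the questionnaires are repeated. If they are, keep the same order at visit two.
4. Clarify that the rule on order of testing applies to the physical tests only.

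The cost is reordering steps within the visit and a short text amendment, with no extra visit, equipment or participants.
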